**Programming Note:**  
 Include all Coagulation Parameters and all scheduled time points.

Clinical cut-off date: DDMMYYYY  
 Program: filepath\_name, Output: filepath\_name (version x.x) Created: DDMMYYYY HH:MM

Table 14.3.4.2.1.1.2 MAD: Summary of Coagulation (Summary of Actual and Change from Baseline Values) by Timepoint  
Protocol: BTI-201  
Safety Population

Clinical cut-off date: DDMMYYYY  
Program: filepath\_name, Output: filepath\_name (version x.x) Created: DDMMYYYY HH:MM

Programming Note:  
Repeat Table 14.3.4.2.1.1  
Include all Coagulation Parameters and all scheduled time points.  
  
Include: rhu-pGSN 6 mg/kg;  
rhu-pGSN 12 mg/kg;  
rhu-pGSN 24 mg/kg;  
Combined Active;  
Combined Placebo;  
Overall

Table 14.3.4.2.2.1 SD: Summary of Coagulation Shifts from Baseline (Low, Normal, High)  
 Protocol: BTI-201  
 Safety Population

Parameter	PT/INR (unit)	Day 2	Result Classification	Baseline 					
				Low n (%)	Normal n (%)	High n (%)	Missing n (%)	Total n (%)	
				rhu-pGGSN: 6 mg/kg (N=xx)					
			Low	xx (xx.x%)	xx (xx.x%)	xx (xx.x%)	xx (xx.x%)	xx (xx.x%)	xx (xx.x%)
			Normal	xx (xx.x%)	xx (xx.x%)	xx (xx.x%)	xx (xx.x%)	xx (xx.x%)	xx (xx.x%)
			High	xx (xx.x%)	xx (xx.x%)	xx (xx.x%)	xx (xx.x%)	xx (xx.x%)	xx (xx.x%)
			Missing	xx (xx.x%)	xx (xx.x%)	xx (xx.x%)	xx (xx.x%)	xx (xx.x%)	xx (xx.x%)
			Total	xx (xx.x%)	xx (xx.x%)	xx (xx.x%)	xx (xx.x%)	xx (xx.x%)	xx (xx.x%)
		Day 3 or 4	Low	xx (xx.x%)	xx (xx.x%)	xx (xx.x%)	xx (xx.x%)	xx (xx.x%)	xx (xx.x%)
			Normal	xx (xx.x%)	xx (xx.x%)	xx (xx.x%)	xx (xx.x%)	xx (xx.x%)	xx (xx.x%)
			High	xx (xx.x%)	xx (xx.x%)	xx (xx.x%)	xx (xx.x%)	xx (xx.x%)	xx (xx.x%)
			Missing	xx (xx.x%)	xx (xx.x%)	xx (xx.x%)	xx (xx.x%)	xx (xx.x%)	xx (xx.x%)
			Total	xx (xx.x%)	xx (xx.x%)	xx (xx.x%)	xx (xx.x%)	xx (xx.x%)	xx (xx.x%)
			etc.						
			etc.						

Note Baseline is defined as the last valid, non-missing assessment prior to first study drug administration. Unscheduled visits not included in post baseline assessments.

Programming Note:  
 Also Include: Placebo,  
 Overall  
 Include all Coagulation Parameters and all scheduled time points.

Table 14.3.4.2.2.2 MAD: Summary of Coagulation Shifts from Baseline (Low, Normal, High)  
Protocol: BTI-201  
Safety Population

Clinical cut-off date: DDMMYYYY  
Program: filepath\_name, Output: filepath\_name (version x.x) Created: DDMMYYYY HH:MM

Programming Note:  
Repeat Table 14.3.4.2.2.1  
Include all Coagulation Parameters and all scheduled time points.  
  
Include: rhu-pGSN 6 mg/kg;  
          rhu-pGSN 12 mg/kg;  
          rhu-pGSN 24 mg/kg;  
          Combined Active;  
          Combined Placebo;  
          Overall

Table 14.3.4.3.1.1.1 SD: Summary of Comprehensive Metabolic Profile (Summary of Actual and Change from Baseline Values) by Timepoint

Protocol: BTI-201  
 Safety Population

Parameter	Visit	rhu-pGSN: 6 mg/kg			Placebo			Overall	
		Actual Value	Change from Baseline 	Actual Value	Change from Baseline 	Actual Value	Change from Baseline 	Actual Value	Change from Baseline 
Sodium (unit)	Baseline 	n	x		x		x		x
		Mean	x.xxx		x.xxx		x.xxx		x.xxx
		Median	x.xxx		x.xxx		x.xxx		x.xxx
		SD	x.xxx		x.xxx		x.xxx		x.xxx
		Minimum	x.xx		x.xx		x.xx		x.xx
Maximum	x.xx		x.xx		x.xx		x.xx		
Day 2	Day 2	n	x		x		x		x
		Mean	x.xxx		x.xxx		x.xxx		x.xxx
		Median	x.xxx		x.xxx		x.xxx		x.xxx
		SD	x.xxx		x.xxx		x.xxx		x.xxx
		Minimum	x.xx		x.xx		x.xx		x.xx
Maximum	x.xx		x.xx		x.xx		x.xx		
Day 3 or 4	Day 3 or 4	n	x		x		x		x
		Mean	x.xxx		x.xxx		x.xxx		x.xxx
		Median	x.xxx		x.xxx		x.xxx		x.xxx
		SD	x.xxx		x.xxx		x.xxx		x.xxx
		Minimum	x.xx		x.xx		x.xx		x.xx
Maximum	x.xx		x.xx		x.xx		x.xx		
etc.									

Note: SD: Standard Deviation

Baseline is defined as the last valid, non-missing assessment prior to first study drug administration. Unscheduled visits not included in post baseline assessments.

Programming Note:  
 Include all Comprehensive Metabolic Profile Parameters and all scheduled time points.

Clinical cut-off date: DDMMYYYY  
 Program: filepath\_name, Output: filepath\_name (version x.x) Created: DDMMYYYY HH:MM

Table 14.3.4.3.1.1.2 MAD: Summary of Comprehensive Metabolic Profile (Summary of Actual and Change from Baseline Values) by Timepoint

Protocol: BTI-201  
Safety Population

Clinical cut-off date: DDMMYYYY  
Program: filepath\_name, Output: filepath\_name (version x.x) Created: DDMMYYYY HH:MM

Programming Note:  
Repeat Table 14.3.4.3.1.1  
Include all Comprehensive Metabolic Profile Parameters and all scheduled time points.  
  
Include: rhu-pGSN 6 mg/kg;  
rhu-pGSN 12 mg/kg;  
rhu-pGSN 24 mg/kg;  
Combined Active;  
Combined Placebo;  
Overall

Table 14.3.4.3.2.1 SD: Summary of Comprehensive Metabolic Profile Shifts from Baseline (Low, Normal, High)  
 Protocol: BTI-201  
 Safety Population

Baseline 							
rhu-pGSN: 6 mg/kg (N=xx)							
Parameter	Day 2	Result Classification	Low n (%)	Normal n (%)	High n (%)	Missing n (%)	Total n (%)
Sodium (unit)	Low						
	Normal		xx (xx.x%)	xx (xx.x%)	xx (xx.x%)	xx (xx.x%)	xx (xx.x%)
	High		xx (xx.x%)	xx (xx.x%)	xx (xx.x%)	xx (xx.x%)	xx (xx.x%)
	Missing		xx (xx.x%)	xx (xx.x%)	xx (xx.x%)	xx (xx.x%)	xx (xx.x%)
Total		xx (xx.x%)	xx (xx.x%)	xx (xx.x%)	xx (xx.x%)	xx (xx.x%)	xx (xx.x%)
Day 3 or 4	Low		xx (xx.x%)	xx (xx.x%)	xx (xx.x%)	xx (xx.x%)	xx (xx.x%)
	Normal		xx (xx.x%)	xx (xx.x%)	xx (xx.x%)	xx (xx.x%)	xx (xx.x%)
	High		xx (xx.x%)	xx (xx.x%)	xx (xx.x%)	xx (xx.x%)	xx (xx.x%)
	Missing		xx (xx.x%)	xx (xx.x%)	xx (xx.x%)	xx (xx.x%)	xx (xx.x%)
Total		xx (xx.x%)	xx (xx.x%)	xx (xx.x%)	xx (xx.x%)	xx (xx.x%)	xx (xx.x%)
etc.							
etc.							

Note Baseline is defined as the last valid, non-missing assessment prior to first study drug administration. Unscheduled visits not included in post baseline assessments.

Programming Note:  
 Also Include: Placebo,  
 Overall  
 Include all Comprehensive Metabolic Profile Parameters and all scheduled time points.

Clinical cut-off date: DDMMYYYY  
 Program: filepath\_name, Output: filepath\_name (version x.x) Created: DDMMYYYY HH:MM

Table 14.3.4.3.2.2 MAD: Summary of Comprehensive Metabolic Profile Shifts from Baseline (Low, Normal, High)  
Protocol: BTI-201  
Safety Population

Clinical cut-off date: DDMMYYYY  
Program: filepath\_name, Output: filepath\_name (version x.x) Created: DDMMYYYY HH:MM

Programming Note:  
Repeat Table 14.3.4.3.2.1  
Include all Comprehensive Metabolic Profile Parameters and all scheduled time points.  
Include: rhu-pGSN 6 mg/kg;  
          rhu-pGSN 12 mg/kg;  
          rhu-pGSN 24 mg/kg;  
          Combined Active;  
          Combined Placebo;  
          Overall

Table 14.3.4.4.1 SD: Summary of Vital Signs (Summary of Actual and Change from Baseline Values) by Timepoint  
 Protocol: BTI-201  
 Safety Population

Parameter	Visit	rhu-pGSN: 6 mg/kg				Overall (N=xx)
		Actual Value	Change from Baseline 	Actual Value	Change from Baseline 	
Systolic blood pressure (mmHg)	Baseline 	n	x	x	x	x
		Mean	x.xxx	x.xxx	x.xxx	x.xxx
		Median	x.xxx	x.xxx	x.xxx	x.xxx
		SD	x.xxx	x.xxx	x.xxx	x.xxx
		Minimum	x.xx	x.xx	x.xx	x.xx
		Maximum	x.xx	x.xx	x.xx	x.xx
Day 1: End of Infusion	Day 1: End of Infusion	n	x	x	x	x
		Mean	x.xxx	x.xxx	x.xxx	x.xxx
		Median	x.xxx	x.xxx	x.xxx	x.xxx
		SD	x.xxx	x.xxx	x.xxx	x.xxx
		Minimum	x.xx	x.xx	x.xx	x.xx
		Maximum	x.xx	x.xx	x.xx	x.xx
etc.	Day 1: 30 mins	n	x	x	x	x
		Mean	x.xxx	x.xxx	x.xxx	x.xxx
		Median	x.xxx	x.xxx	x.xxx	x.xxx
		SD	x.xxx	x.xxx	x.xxx	x.xxx
		Minimum	x.xx	x.xx	x.xx	x.xx
		Maximum	x.xx	x.xx	x.xx	x.xx

Note: SD: Standard Deviation

Baseline is defined as the last valid, non-missing assessment prior to first study drug administration. Unscheduled visits not included in post baseline assessments.

Programming Note:  
 Include all Vital Signs Parameters and all time points.

Clinical cut-off date: DDMMYYYY  
 Program: filepath\_name, Output: filepath\_name (version x.x) Created: DDMMYYYY HH:MM

Table 14.3.4.4.2 MAD: Summary of Vital Signs (Summary of Actual and Change from Baseline Values) by Timepoint  
Protocol: BTI-201  
Safety Population

Clinical cut-off date: DDMMYYYY  
Program: filepath\_name, Output: filepath\_name (version x.x) Created: DDMMYYYY HH:MM

Programming Note:  
Repeat Table 14.3.4.4.1  
Include all Vital Sign Parameters and all scheduled time points.  
  
Include: rhu-pGSN 6 mg/kg;  
          rhu-pGSN 12 mg/kg;  
          rhu-pGSN 24 mg/kg;  
          Combined Active;  
          Combined Placebo;  
          Overall

Table 14.3.4.5.1 SD: Summary of Vital Signs Interpretation by Timepoint  
 Protocol: BTI-201  
 Safety Population

Visit		rhu-pGSN: (N=xx)	6 mg/kg	Placebo (N=xx)	Overall (N=xx)
Baseline 	n	xx		xx	xx
	Normal	xx (xx.x%)		xx (xx.x%)	xx (xx.x%)
	Abnormal NCS	xx (xx.x%)		xx (xx.x%)	xx (xx.x%)
	Abnormal CS	xx (xx.x%)		xx (xx.x%)	xx (xx.x%)
Day 1: 30 mins	n	xx		xx	xx
	Normal	xx (xx.x%)		xx (xx.x%)	xx (xx.x%)
	Abnormal NCS	xx (xx.x%)		xx (xx.x%)	xx (xx.x%)
	Abnormal CS	xx (xx.x%)		xx (xx.x%)	xx (xx.x%)
Day 2	n	xx		xx	xx
	Normal	xx (xx.x%)		xx (xx.x%)	xx (xx.x%)
	Abnormal NCS	xx (xx.x%)		xx (xx.x%)	xx (xx.x%)
	Abnormal CS	xx (xx.x%)		xx (xx.x%)	xx (xx.x%)
etc.					

Note: SD: Standard Deviation

Baseline is defined as the last valid, non-missing assessment prior to first study drug administration.  
 NCS = Not Clinically Significant; CS = Clinically Significant.  
 Unscheduled visits not included in post baseline assessments.

Clinical cut-off date: DDMMYYYY  
 Program: filepath\_name, Output: filepath\_name (version x.x) Created: DDMMYYYY HH:MM

Table 14.3.4.5.2 MAD: Summary of Vital Signs Interpretation by Timepoint  
Protocol: BTI-201  
Safety Population

Clinical cut-off date: DDMMYYYY  
Program: filepath\_name, Output: filepath\_name (version x.x) Created: DDMMYYYY HH:MM

Programming Note:  
Repeat Table 14.3.4.5.1  
Include all scheduled time points.  
  
Include: rhu-pGSN 6 mg/kg;  
          rhu-pGSN 12 mg/kg;  
          rhu-pGSN 24 mg/kg;  
          Combined Active;  
          Combined Placebo;  
          Overall

Table 14.3.4.6.1 SD: Summary of Mean EKG (Summary of Actual and Change from Baseline Values) by Timepoint  
 Protocol: BTI-201  
 Safety Population

Parameter	Visit	rhu-pGSN: 6 mg/kg				Overall (N=xx)
		Actual Value	Change from Baseline 	Actual Value	Change from Baseline 	
Heart Rate (unit)	Baseline 	n	x	x	x	x
		Mean	x.xxx	x.xxx	x.xxx	x.xxx
		Median	x.xxx	x.xxx	x.xxx	x.xxx
		SD	x.xxx	x.xxx	x.xxx	x.xxx
		Minimum	x.xx	x.xx	x.xx	x.xx
		Maximum	x.xx	x.xx	x.xx	x.xx
	Day 28 / Early Termination	n	x	x	x	x
		Mean	x.xxx	x.xxx	x.xxx	x.xxx
		Median	x.xxx	x.xxx	x.xxx	x.xxx
		SD	x.xxx	x.xxx	x.xxx	x.xxx
		Minimum	x.xx	x.xx	x.xx	x.xx
		Maximum	x.xx	x.xx	x.xx	x.xx
PR Interval (unit)	Baseline 	n	x	x	x	x
		Mean	x.xxx	x.xxx	x.xxx	x.xxx
		Median	x.xxx	x.xxx	x.xxx	x.xxx
		SD	x.xxx	x.xxx	x.xxx	x.xxx
		Minimum	x.xx	x.xx	x.xx	x.xx
		Maximum	x.xx	x.xx	x.xx	x.xx
etc.	etc.					

Note: SD: Standard Deviation

Baseline is defined as the last valid, non-missing assessment prior to first study drug administration.  
 Unscheduled visits not included in post baseline assessments.

Programming Note:  
 Include all EKG Parameters and all time points.

Clinical cut-off date: DDMMYYYY  
 Program: filepath\_name, Output: filepath\_name (version x.x) Created: DDMMYYYY HH:MM

Table 14.3.4.6.2 MAD: Summary of Mean EKG (Summary of Actual and Change from Baseline Values) by Timepoint  
Protocol: BTI-201  
Safety Population

Clinical cut-off date: DDMMYYYY  
Program: filepath\_name, Output: filepath\_name (version x.x) Created: DDMMYYYY HH:MM

Programming Note:  
Repeat Table 14.3.4.6.1  
Include all EKG Parameters and all scheduled time points.  
  
Include: rhu-pGSN 6 mg/kg;  
          rhu-pGSN 12 mg/kg;  
          rhu-pGSN 24 mg/kg;  
          Combined Active;  
          Combined Placebo;  
          Overall

Table 14.3.4.7.1 SD: Summary of EKG Interpretation (Worst) by Timepoint  
 Protocol: BTI-201  
 Safety Population

Visit	n	rhu-pGSN: 6 mg/kg (N=xx)	Placebo (N=xx)	Overall (N=xx)
Baseline 				
Normal	xx (xx.x%)	xx (xx.x%)	xx (xx.x%)	xx (xx.x%)
Abnormal NCS	xx (xx.x%)	xx (xx.x%)	xx (xx.x%)	xx (xx.x%)
Abnormal CS	xx (xx.x%)	xx (xx.x%)	xx (xx.x%)	xx (xx.x%)
Day 28 / Early Termination				
Normal	xx (xx.x%)	xx (xx.x%)	xx (xx.x%)	xx (xx.x%)
Abnormal NCS	xx (xx.x%)	xx (xx.x%)	xx (xx.x%)	xx (xx.x%)
Abnormal CS	xx (xx.x%)	xx (xx.x%)	xx (xx.x%)	xx (xx.x%)

Note: SD: Standard Deviation

Baseline is defined as the last valid, non-missing assessment prior to first study drug administration.  
 NCS = Not Clinically Significant; CS = Clinically Significant.  
 Unscheduled visits not included in post baseline assessments.

Clinical cut-off date: DDMMYYYY  
 Program: filepath\_name, Output: filepath\_name (version x.x) Created: DDMMYYYY HH:MM

Table 14.3.4.7.2 MAD: Summary of EKG Interpretation (Worst) by Timepoint  
Protocol: BTI-201  
Safety Population

Clinical cut-off date: DDMMYYYY  
Program: filepath\_name, Output: filepath\_name (version x.x) Created: DDMMYYYY HH:MM

Programming Note:  
Repeat Table 14.3.4.7.1

Include: rhu-pGSN 6 mg/kg;  
rhu-pGSN 12 mg/kg;  
rhu-pGSN 24 mg/kg;  
Combined Active;  
Combined Placebo;  
Overall

Table 14.3.4.8.1 SD: Summary of CURB-65 Score (Summary of Actual and Change from Baseline Values) by Timepoint  
 Protocol: BTI-201  
 Safety Population

Visit	rhu-pGSN: 6 mg/kg			Placebo			Overall		
	Actual Value	Change from Baseline 	Actual Value	Change from Baseline 	Actual Value	Change from Baseline 	Actual Value	Change from Baseline 	
Baseline 	n	x	x	x	x	x	x	x	
	Mean	x.xxx	x.xxx	x.xxx	x.xxx	x.xxx	x.xxx	x.xxx	
	Median	x.xxx	x.xxx	x.xxx	x.xxx	x.xxx	x.xxx	x.xxx	
	SD	x.xxx	x.xxx	x.xxx	x.xxx	x.xxx	x.xxx	x.xxx	
	Minimum	x.xx	x.xx	x.xx	x.xx	x.xx	x.xx	x.xx	
	Maximum	x.xx	x.xx	x.xx	x.xx	x.xx	x.xx	x.xx	
Day 3 or 4	n	x	x	x	x	x	x	x	
	Mean	x.xxx	x.xxx	x.xxx	x.xxx	x.xxx	x.xxx	x.xxx	
	Median	x.xxx	x.xxx	x.xxx	x.xxx	x.xxx	x.xxx	x.xxx	
	SD	x.xxx	x.xxx	x.xxx	x.xxx	x.xxx	x.xxx	x.xxx	
	Minimum	x.xx	x.xx	x.xx	x.xx	x.xx	x.xx	x.xx	
	Maximum	x.xx	x.xx	x.xx	x.xx	x.xx	x.xx	x.xx	
Day 7	n	x	x	x	x	x	x	x	
	Mean	x.xxx	x.xxx	x.xxx	x.xxx	x.xxx	x.xxx	x.xxx	
	Median	x.xxx	x.xxx	x.xxx	x.xxx	x.xxx	x.xxx	x.xxx	
	SD	x.xxx	x.xxx	x.xxx	x.xxx	x.xxx	x.xxx	x.xxx	
	Minimum	x.xx	x.xx	x.xx	x.xx	x.xx	x.xx	x.xx	
	Maximum	x.xx	x.xx	x.xx	x.xx	x.xx	x.xx	x.xx	
etc.									

Note: SD: Standard Deviation

Baseline is defined as the last valid, non-missing assessment prior to first study drug administration. Unscheduled visits not included in post baseline assessments.

Programming Note:  
 Include all scheduled time points.

Clinical cut-off date: DMMMMYYY  
 Program: filepath\_name, Output: filepath\_name (version x.x) Created: DMMMMYYY HH:MM

Table 14.3.4.8.2 MAD: Summary of CURB-65 Score (Summary of Actual and Change from Baseline Values) by Timepoint  
Protocol: BTI-201  
Safety Population

Clinical cut-off date: DDMMYYYY  
Program: filepath\_name, Output: filepath\_name (version x.x) Created: DDMMYYYY HH:MM

Programming Note:  
Repeat Table 14.3.4.8.1  
Include all scheduled time points.  
  
Include: rhu-pGSN 6 mg/kg;  
          rhu-pGSN 12 mg/kg;  
          rhu-pGSN 24 mg/kg;  
          Combined Active;  
          Combined Placebo;  
          Overall

Table 14.3.4.9.1 SD: Summary of PSI Score (Summary of Actual and Change from Baseline Values) by Timepoint  
 Protocol: BTI-201  
 Safety Population

Visit	rhu-pGSN: 6 mg/kg			Placebo			Overall	
	Actual Value	Change from Baseline 	Actual Value	Change from Baseline 	Actual Value	Change from Baseline 	Actual Value	Change from Baseline 
Baseline 	n	x	x	x	x	x	x	x
	Mean	x.xxx	x.xxx	x.xxx	x.xxx	x.xxx	x.xxx	x.xxx
	Median	x.xxx	x.xxx	x.xxx	x.xxx	x.xxx	x.xxx	x.xxx
	SD	x.xxx	x.xxx	x.xxx	x.xxx	x.xxx	x.xxx	x.xxx
	Minimum	x.xx	x.xx	x.xx	x.xx	x.xx	x.xx	x.xx
	Maximum	x.xx	x.xx	x.xx	x.xx	x.xx	x.xx	x.xx
Day 3 or 4	n	x	x	x	x	x	x	x
	Mean	x.xxx	x.xxx	x.xxx	x.xxx	x.xxx	x.xxx	x.xxx
	Median	x.xxx	x.xxx	x.xxx	x.xxx	x.xxx	x.xxx	x.xxx
	SD	x.xxx	x.xxx	x.xxx	x.xxx	x.xxx	x.xxx	x.xxx
	Minimum	x.xx	x.xx	x.xx	x.xx	x.xx	x.xx	x.xx
	Maximum	x.xx	x.xx	x.xx	x.xx	x.xx	x.xx	x.xx
Day 7	n	x	x	x	x	x	x	x
	Mean	x.xxx	x.xxx	x.xxx	x.xxx	x.xxx	x.xxx	x.xxx
	Median	x.xxx	x.xxx	x.xxx	x.xxx	x.xxx	x.xxx	x.xxx
	SD	x.xxx	x.xxx	x.xxx	x.xxx	x.xxx	x.xxx	x.xxx
	Minimum	x.xx	x.xx	x.xx	x.xx	x.xx	x.xx	x.xx
	Maximum	x.xx	x.xx	x.xx	x.xx	x.xx	x.xx	x.xx
etc.								

Note: SD: Standard Deviation

Baseline is defined as the last valid, non-missing assessment prior to first study drug administration. Unscheduled visits not included in post baseline assessments.

Programming Note:  
 Include all scheduled time points.

Clinical cut-off date: DDMMYYYY  
 Program: filepath\_name, Output: filepath\_name (version x.x) Created: DDMMYYYY HH:MM

Table 14.3.4.9.2 MAD: Summary of PSI Score (Summary of Actual and Change from Baseline Values) by Timepoint  
Protocol: BTI-201  
Safety Population

Clinical cut-off date: DDMMYYYY  
Program: filepath\_name, Output: filepath\_name (version x.x) Created: DDMMYYYY HH:MM

Programming Note:  
Repeat Table 14.3.4.9.1  
Include all scheduled time points.  
  
Include: rhu-pGSN 6 mg/kg;  
          rhu-pGSN 12 mg/kg;  
          rhu-pGSN 24 mg/kg;  
          Combined Active;  
          Combined Placebo;  
          Overall

Table 14.3.4.10.1 SD: Summary of PSI Risk Class by Timepoint  
 Protocol: BTI-201  
 Safety Population

Visit	Risk Class	rhu-pGSN: 6 mg/kg (N=xx)	Placebo (N=xx)	Overall (N=xx)
Baseline 	n	xx	xx	xx
	Class I	xx (xx.x%)	xx (xx.x%)	xx (xx.x%)
	Class II	xx (xx.x%)	xx (xx.x%)	xx (xx.x%)
	Class III	xx (xx.x%)	xx (xx.x%)	xx (xx.x%)
	Class IV	xx (xx.x%)	xx (xx.x%)	xx (xx.x%)
	Class V	xx (xx.x%)	xx (xx.x%)	xx (xx.x%)
Day 28 / Early Termination	n	xx	xx	xx
	Class I	xx (xx.x%)	xx (xx.x%)	xx (xx.x%)
	Class II	xx (xx.x%)	xx (xx.x%)	xx (xx.x%)
	Class III	xx (xx.x%)	xx (xx.x%)	xx (xx.x%)
	Class IV	xx (xx.x%)	xx (xx.x%)	xx (xx.x%)
	Class V	xx (xx.x%)	xx (xx.x%)	xx (xx.x%)

Note: SD: Standard Deviation

Baseline is defined as the last valid, non-missing assessment prior to first study drug administration.  
 NCS = Not Clinically Significant; CS = Clinically Significant.  
 Unscheduled visits not included in post baseline assessments.

Clinical cut-off date: DDDMMYYYY  
 Program: filepath\_name, Output: filepath\_name (version x.x) Created: DDDMMYYYY HH:MM

Table 14.3.4.10.2 MAD: Summary of PSI Risk Class by Timepoint  
Protocol: BTI-201  
Safety Population

Clinical cut-off date: DDMMYYYY  
Program: filepath\_name, Output: filepath\_name (version x.x) Created: DDMMYYYY HH:MM

Programming Note:  
Repeat Table 14.3.4.10.1  
Include all scheduled time points.  
  
Include: rhu-pGSN 6 mg/kg;  
          rhu-pGSN 12 mg/kg;  
          rhu-pGSN 24 mg/kg;  
          Combined Active;  
          Combined Placebo;  
          Overall

Table 14.3.4.11.1.1 SD: Summary of SOFA Score (Summary of Actual and Change from Baseline Values) by Timepoint  
 Protocol: BTI-201  
 Safety Population

Visit	rhu-pGSN: 6 mg/kg			Placebo			Overall		
	Actual Value	Change from Baseline 	Actual Value	Change from Baseline 	Actual Value	Change from Baseline 	Actual Value	Change from Baseline 	
Baseline 	n	x	x	x	x	x	x	x	
	Mean	x.xxx	x.xxx	x.xxx	x.xxx	x.xxx	x.xxx	x.xxx	
	Median	x.xxx	x.xxx	x.xxx	x.xxx	x.xxx	x.xxx	x.xxx	
	SD	x.xxx	x.xxx	x.xxx	x.xxx	x.xxx	x.xxx	x.xxx	
	Minimum	x.xx	x.xx	x.xx	x.xx	x.xx	x.xx	x.xx	
	Maximum	x.xx	x.xx	x.xx	x.xx	x.xx	x.xx	x.xx	
Day 3 or 4	n	x	x	x	x	x	x	x	
	Mean	x.xxx	x.xxx	x.xxx	x.xxx	x.xxx	x.xxx	x.xxx	
	Median	x.xxx	x.xxx	x.xxx	x.xxx	x.xxx	x.xxx	x.xxx	
	SD	x.xxx	x.xxx	x.xxx	x.xxx	x.xxx	x.xxx	x.xxx	
	Minimum	x.xx	x.xx	x.xx	x.xx	x.xx	x.xx	x.xx	
	Maximum	x.xx	x.xx	x.xx	x.xx	x.xx	x.xx	x.xx	
Day 7	n	x	x	x	x	x	x	x	
	Mean	x.xxx	x.xxx	x.xxx	x.xxx	x.xxx	x.xxx	x.xxx	
	Median	x.xxx	x.xxx	x.xxx	x.xxx	x.xxx	x.xxx	x.xxx	
	SD	x.xxx	x.xxx	x.xxx	x.xxx	x.xxx	x.xxx	x.xxx	
	Minimum	x.xx	x.xx	x.xx	x.xx	x.xx	x.xx	x.xx	
	Maximum	x.xx	x.xx	x.xx	x.xx	x.xx	x.xx	x.xx	
etc.									

Note: SD: Standard Deviation

Baseline is defined as the last valid, non-missing assessment prior to first study drug administration. Unscheduled visits not included in post baseline assessments.

Programming Note:  
 Include all scheduled time points.

Clinical cut-off date: DDMMYYYY  
 Program: filepath\_name, Output: filepath\_name (version x.x) Created: DDMMYYYY HH:MM

Table 14.3.4.11.2 MAD: Summary of SOFA Score (Summary of Actual and Change from Baseline Values) by Timepoint  
Protocol: BTI-201  
Safety Population

Clinical cut-off date: DDMMYYYY  
Program: filepath\_name, Output: filepath\_name (version x.x) Created: DDMMYYYY HH:MM

Programming Note:  
Repeat Table 14.3.4.11.1  
Include all scheduled time points.  
  
Include: rhu-pGSN 6 mg/kg;  
          rhu-pGSN 12 mg/kg;  
          rhu-pGSN 24 mg/kg;  
          Combined Active;  
          Combined Placebo;  
          Overall

Table 14.3.4.12.1.1 SD: Summary of MMSE Score (Summary of Actual and Change from Baseline Values) by Timepoint  
 Protocol: BTI-201  
 Safety Population

Visit	rhu-pGSN: 6 mg/kg			Placebo			Overall		
	Actual Value	Change from Baseline 	Actual Value	Change from Baseline 	Actual Value	Change from Baseline 	Actual Value	Change from Baseline 	
Baseline 	n	x	x	x	x	x	x	x	
	Mean	x.xxx	x.xxx	x.xxx	x.xxx	x.xxx	x.xxx	x.xxx	
	Median	x.xxx	x.xxx	x.xxx	x.xxx	x.xxx	x.xxx	x.xxx	
	SD	x.xxx	x.xxx	x.xxx	x.xxx	x.xxx	x.xxx	x.xxx	
	Minimum	x.xx	x.xx	x.xx	x.xx	x.xx	x.xx	x.xx	
	Maximum	x.xx	x.xx	x.xx	x.xx	x.xx	x.xx	x.xx	
Day 3 or 4	n	x	x	x	x	x	x	x	
	Mean	x.xxx	x.xxx	x.xxx	x.xxx	x.xxx	x.xxx	x.xxx	
	Median	x.xxx	x.xxx	x.xxx	x.xxx	x.xxx	x.xxx	x.xxx	
	SD	x.xxx	x.xxx	x.xxx	x.xxx	x.xxx	x.xxx	x.xxx	
	Minimum	x.xx	x.xx	x.xx	x.xx	x.xx	x.xx	x.xx	
	Maximum	x.xx	x.xx	x.xx	x.xx	x.xx	x.xx	x.xx	
Day 7	n	x	x	x	x	x	x	x	
	Mean	x.xxx	x.xxx	x.xxx	x.xxx	x.xxx	x.xxx	x.xxx	
	Median	x.xxx	x.xxx	x.xxx	x.xxx	x.xxx	x.xxx	x.xxx	
	SD	x.xxx	x.xxx	x.xxx	x.xxx	x.xxx	x.xxx	x.xxx	
	Minimum	x.xx	x.xx	x.xx	x.xx	x.xx	x.xx	x.xx	
	Maximum	x.xx	x.xx	x.xx	x.xx	x.xx	x.xx	x.xx	
etc.									

Note: SD: Standard Deviation

Baseline is defined as the last valid, non-missing assessment prior to first study drug administration. Unscheduled visits not included in post baseline assessments.

Programming Note:  
 Include all scheduled time points.

Clinical cut-off date: DDMMYYYY  
 Program: filepath\_name, Output: filepath\_name (version x.x) Created: DDMMYYYY HH:MM

Table 14.3.4.12.2 MAD: Summary of MMSE Score (Summary of Actual and Change from Baseline Values) by Timepoint  
Protocol: BTI-201  
Safety Population

Clinical cut-off date: DDMMYYYY  
Program: filepath\_name, Output: filepath\_name (version x.x) Created: DDMMYYYY HH:MM

Programming Note:  
Repeat Table 14.3.4.12.1  
Include all scheduled time points.  
  
Include: rhu-pGSN 6 mg/kg;  
          rhu-pGSN 12 mg/kg;  
          rhu-pGSN 24 mg/kg;  
          Combined Active;  
          Combined Placebo;  
          Overall

Table 14.3.4.13.1 SD: Summary of Hospitalization  
 Protocol: BTI-201  
 Safety Population

Parameter (Kaplan-Meier Estimates)	rhu-pGSN: 6 mg/kg (N=xx)	Placebo (N=xx)	Overall (N=xx)
Hospital Stay			
Number of Subjects Discharged	xx (xx.x%)	xx (xx.x%)	xx (xx.x%)
Number of Subjects not Discharged	xx (xx.x%)	xx (xx.x%)	xx (xx.x%)
Length of Stay in Hospital (hours) (95% CI)			
25th Percentile	xx (xx.x, xx.x)	xx (xx.x, xx.x)	xx (xx.x, xx.x)
Median	xx (xx.x, xx.x)	xx (xx.x, xx.x)	xx (xx.x, xx.x)
75th Percentile	xx (xx.x, xx.x)	xx (xx.x, xx.x)	xx (xx.x, xx.x)
ICU Stay			
Number of Subjects in ICU	xx (xx.x%)	xx (xx.x%)	xx (xx.x%)
Number of Subjects not in ICU	xx (xx.x%)	xx (xx.x%)	xx (xx.x%)
Length of Stay in ICU (days) (95% CI)			
25th Percentile	xx (xx.x, xx.x)	xx (xx.x, xx.x)	xx (xx.x, xx.x)
Median	xx (xx.x, xx.x)	xx (xx.x, xx.x)	xx (xx.x, xx.x)
75th Percentile	xx (xx.x, xx.x)	xx (xx.x, xx.x)	xx (xx.x, xx.x)
Intubation			
Number of Subjects Intubated	xx (xx.x%)	xx (xx.x%)	xx (xx.x%)
Number of Subjects not Intubated	xx (xx.x%)	xx (xx.x%)	xx (xx.x%)
Length of Intubation (days) (95% CI)			
25th Percentile	xx (xx.x, xx.x)	xx (xx.x, xx.x)	xx (xx.x, xx.x)
Median	xx (xx.x, xx.x)	xx (xx.x, xx.x)	xx (xx.x, xx.x)
75th Percentile	xx (xx.x, xx.x)	xx (xx.x, xx.x)	xx (xx.x, xx.x)

Note: CI = Confidence Interval; Brookmeyer and Crowley method (1982, Log-log transformation);  
 Length of stay in hospital is defined as the date and time of discharge/date of study exit (23:59 PM) -  
 date and time of hospitalization admission due to CAP in hours

Clinical cut-off date: DDMMYYYY  
 Program: filepath\_name, Output: filepath\_name (version x.x) Created: DDMMYYYY HH:MM

Table 14.3.4.13.2 MAD: Summary of Hospitalization  
Protocol: BTI-201  
Safety Population

Clinical cut-off date: DDMMYYYY  
Program: filepath\_name, Output: filepath\_name (version x.x) Created: DDMMYYYY HH:MM

Programming Note:  
Repeat Table 14.3.4.13.1  
Include all scheduled time points.  
  
Include: rhu-pGSN 6 mg/kg;  
          rhu-pGSN 12 mg/kg;  
          rhu-pGSN 24 mg/kg;  
          Combined Active;  
          Combined Placebo;  
          Overall

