5.2. Endpoints

5.2.1. Primary Endpoint

- Incidence, causality, and severity of AEs and SAEs graded according to the National Cancer Institute (NCI) Common Terminology Criteria for Adverse Events (CTCAE) version 4.03 (or equivalent), clinically significant laboratory and/or electrocardiogram (EKG) abnormalities, death irrespective of cause, cause of death per investigator, including relationship to study drug; use of vasopressors, intubation, or transfer to the ICU or equivalent through Day 7

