5.2.2. Secondary Endpoints

- PK for rhu-pGSN including, but not limited to maximum concentration (C_{max}), time to maximum concentration (T_{max}), terminal half-life ($T_{1/2}$), area under the curve from time zero to 8 hours (AUC_{0-8}), area under the curve from time zero to infinity (AUC_{inf}) (levels measured within 30 minutes predose, 5-10 minutes after the end of administration, and 2, 8, 12 and/or 16, and 24 hours (\pm 30 minutes) after each dose (Day 3 sampling in multiple-dose arms is optional)

- Incidence, causality, and severity of AEs and SAEs graded according to the NCI CTCAE version 4.03 (or equivalent); clinically significant laboratory and/or EKG abnormalities as required by SOC; death irrespective of cause; cause of death per investigator, including relationship to study drug; use of vasopressors, intubation, or transfer to the ICU or equivalent through Day 28 (secondary time point)

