The laboratory result tables will present summary statistics for each laboratory parameter within the specific test panel. For each parameter, summaries will be presented for the baseline and each scheduled post-baseline visit. In addition, summaries will be presented for the change from baseline values at each scheduled post-baseline visit.

Additionally, counts (%) of number subjects with values out of normal range at each scheduled time point will also be presented along with shift tables that will represent the changes in normal range categories across post-baseline time points.

The listings of laboratory parameters will include all the information (fields) collected. In addition, the observations that are used as the baseline record (value) for each parameter will be flagged, and the change from baseline values at each post-baseline visit will be presented.

For all parameters, standardized values will be reported.

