### **11.4.2 Biostatistical Methods**

All EKG data collected at scheduled and unscheduled visits will be included in the listings, but only results collected as scheduled visits will be included in the summary tables.

The parameter names that will be used in the outputs will comprise of the test name and the unit of measure, for example, 'Heart Rate (beats/min)'. Parameters will be sorted in the order that the measurements were collected in on the EKG eCRF page within the tables and listings.

For study visits where, multiple EKG measurement are taken, the mean of the measurements will be summarized and the worst-case overall investigator interpretation for the multiple measurements will be presented.

The change from baseline to the pre-dose assessment at each post-baseline visit will be calculated for all parameters.

The decimal precision for each parameter will be based on the maximum number of decimals to which the results were reported on the eCRF.

EKG measurements will present summary statistics for the results at the baseline and each scheduled post-baseline visit for each of the parameters. In addition, summaries will be presented for the change from baseline values at each scheduled post-baseline visit.

The summary of overall interpretation results table will present counts and percentages for the reported results at baseline and each post-baseline visit/time point. Result categories will be ordered as 'Normal', 'Abnormal NCS' and 'Abnormal CS'.

The listings of EKG measurements will include all the information collected and calculated (mean results). In addition, the observations that are used as the baseline record (value) for each parameter will be flagged, and the change from baseline values at each post-baseline visit will be presented.

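### The EKG interpretation summary gives unlinked counts at baseline and Day 28/Early Termination, so no summary table identifies new clinically significant EKG abnormalities

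*SAP*

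**What the plan says.** Protocol 5.2.1 includes "clinically significant laboratory and/or electrocardiogram (EKG) abnormalities" in the primary endpoint, whose window closes with "use of vasopressors, intubation, or transfer to the ICU or equivalent through Day 7". Protocol 5.2.2 repeats the component as a secondary endpoint, ending with "transfer to the ICU or equivalent through Day 28 (secondary time point", and there ties laboratory and EKG abnormalities to what standard of care requires.

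For the EKG interpretation, SAP 11.4.2 states: "The summary of overall interpretation results table will present counts and percentages for the reported results at baseline and each post-baseline visit/time point". The mock shell, "Table 14.3.4.7.1 SD: Summary of EKG Interpretation (Worst) by Timepoint", has two blocks, Baseline and Day 28/Early Termination, each with Normal, Abnormal NCS and Abnormal CS counts. Table 14.3.4.7.2 repeats it for the multiple-dose cohorts. The word Worst in the title refers to the worst reading among replicate tracings at one visit, not the worst across visits. SAP 11.4.2 keeps unscheduled tracings out of the summaries: "All EKG data collected at scheduled and unscheduled visits will be included in the listings, but only results collected as scheduled visits will be included".

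Laboratory data are treated differently. SAP 11.2.2 now adds "shift tables that will represent the changes in normal range categories across post-baseline time points", with shells for blood count, coagulation and metabolic profile (for example Table 14.3.4.1.2.1). The table list in SAP section 17 has no shift table for EKG interpretation. It has none for vital-sign interpretation either, where the shell is "Table 14.3.4.5.1 SD: Summary of Vital Signs Interpretation by Timepoint".

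**The concern.** A safety component framed around incidence asks how many subjects became abnormal after dosing. Two separate sets of counts give prevalence at two times. A Day 28 CS count mixes abnormalities present before dosing with ones that arose later, and equal counts before and after are compatible with no new findings or with several.

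Pre-existing abnormality is plausible here. Protocol 7.3 excludes active heart failure, infarction and embolism and recent cardiopulmonary arrest, but not a history of heart disease, and congestive heart failure is a scored item in the Pneumonia Severity Index (Protocol Appendix C). Subjects are also acutely ill at baseline, so old findings may resolve while new ones appear. At stake is whether the report can state a pre-specified count and denominator for new CS EKG findings, or must rely on someone counting them from listings.

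**Working it through.** The plan states no figure to reproduce. The check has two parts.

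**1. Do the two blocks determine the number of new CS subjects?**

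Let n be the subjects with results at both visits, b the number CS at baseline and d the number CS at Day 28/Early Termination. A new CS subject is not CS at baseline and CS at follow-up. Given only n, b and d:

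- smallest possible number = max(0, d − b)
- largest possible number = min(d, n − b)

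Group sizes come from the design: 6 active subjects per cohort, and 3 × 6 = 18 active subjects in the multiple-dose cohorts combined. The values of b and d below are assumptions for illustration; the documents give none.

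| n | b | d | Smallest | Largest | Not CS at baseline |
|---|---|---|---|---|---|
| 6 | 0 | 1 | max(0, 1) = 1 | min(1, 6) = 1 | 6 |
| 6 | 1 | 1 | max(0, 0) = 0 | min(1, 5) = 1 | 5 |
| 6 | 2 | 2 | max(0, 0) = 0 | min(2, 4) = 2 | 4 |
| 18 | 5 | 5 | max(0, 0) = 0 | min(5, 13) = 5 | 13 |

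For n = 6 and b = d = 2, the new-onset proportion could be anywhere from 0/4 = 0% to 2/4 = 50%.

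The two limits differ exactly when b and d both lie between 1 and n − 1. That is (n − 1)² of the (n + 1)² possible pairs: 25 of 49 (51%) for n = 6, and 289 of 361 (80%) for n = 18. These are shares of possible pairs, not probabilities. If nobody is CS at baseline, the planned table is exact.

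Missing follow-up adds to the uncertainty, because SAP section 3 bases percentages on non-missing results and the two blocks need not hold the same subjects. Take 6 subjects with 2 CS at baseline, 5 Day 28 results and 2 CS among those 5:

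- Missing subject was CS at baseline: 4 at risk, with 1 to 2 new.
- Missing subject was not CS at baseline: 3 at risk, with 0 to 2 new.

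The possible proportion now runs from 0% to 2/3 = 67%, and the denominator itself is unknown.

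**2. Which endpoint does the table serve?**

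Protocol Tables 5 and 6 schedule EKGs at screening, on Day 1 before treatment, and at Day 28/early termination. Apart from an early-termination tracing taken by Day 7, no scheduled post-dose EKG falls in the primary window. An unscheduled tracing within Day 7 is listed but not tabulated. The planned table therefore informs the Day 28 secondary time point.

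**The case against.** The strongest reply is that the information is not lost. Listings 16.2.10.1/2 show each subject's interpretation by visit, flag the baseline record and include unscheduled tracings. With 6 active and 2 placebo subjects per cohort, every transition can be read by hand. This stands. A reader might infer from the summary table that new CS findings cannot be told from old ones anywhere in the outputs; the listings rule that reading out.

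A second reply is that new events reach the adverse-event tables, since SAP 11.1.1 defines treatment-emergent events as those arising or worsening after the first dose. This stands in part. Protocol 9.2.6 tells sites to report clinically significant laboratory results as adverse events, and 9.2.2 has a similar rule for vital signs that meet the adverse-event definition. The EKG section, 9.2.5, has no such sentence, so this route is less certain for EKGs. It also gives no denominator of subjects free of a CS finding at baseline.

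A third reply is that the Day 7 primary component is not what this table reports. This also stands, given the EKG schedule. A Day 28 shift table alone would not supply the primary component.

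Finally, vital signs are not named in the primary endpoint, and Tables 14.3.4.4.1/2 already give their change from baseline. Replacing the by-timepoint interpretation table would lose the post-injection rows. So the vital-sign display is at most an optional addition.

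**Conclusion.** The point holds as a gap in the summary tables. New CS EKG abnormalities cannot be counted from Tables 14.3.4.7.1/2 whenever some, but not all, subjects in a group are CS at each visit. They are visible only in listings or, if reported, as treatment-emergent events. The gap mainly affects the Day 28 secondary endpoint.

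The documents do not support the further inference that the primary endpoint is unassessable because of this table, since the table holds almost no data from the primary window.

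The size depends on how many subjects are CS at baseline, which is unknown: none if baseline is clean, and 0 to 2 new subjects in an arm of 6 under the assumed counts of 2 and 2. In a small descriptive study with full listings this is a modest fault. It is still worth correcting, because a named endpoint component should have a pre-specified count and denominator, and the SAP already uses the remedy for all three laboratory panels.

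**What to change.** 1. Add, for each treatment group, a shift table of baseline EKG category (Normal, Abnormal NCS, Abnormal CS, Missing) by Day 28/Early Termination category, laid out like Table 14.3.4.1.2.1, for both the single-dose and multiple-dose parts.
2. Add one row: subjects newly CS over subjects not CS at baseline who have a post-baseline result. Use the worst post-baseline tracing, including unscheduled EKGs, and show the row through Day 7 and through Day 28. This needs a stated exception to the rule in SAP 11.4.2 that keeps unscheduled results out of summaries. Print the denominator, because most Day 7 tracings will exist only where care prompted one.
3. Optionally, add the same shift display for vital-sign interpretation alongside Tables 14.3.4.5.1/2, not in place of them.

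One limit remains. A subject who is CS at both visits may have the same abnormality or a different new one, and the listing must settle which.

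The cost is a new shell and a small amount of programming on data already collected.
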